#### **5.6.3. Adjustment for Multiple Comparison**

The following multiplicity adjustment approach, a hierarchical procedure, will be used to control the overall Type-1 error rate at 0.05 for the primary endpoint and the secondary endpoints across the 2 dupilumab dose regimens versus placebo. Each hypothesis will be formally tested only if the preceding one is significant at the 2-sided 0.05 significance level. The hierarchical testing order is shown as below (all comparisons are with the placebo).

		Dupilumab	
		300mg QW group	300mg Q2W group
Endpoints			
Co-Primary endpoints	Proportion of patients achieving peak esophageal intraepithelial eosinophil count of $\leq 6$ eos/hpf at week 24	1	3
	Absolute change in DSQ score from baseline to week 24		
Secondary endpoints	Percent change in DSQ from baseline to week 24	2	4
	Percent change in peak esophageal intraepithelial eosinophil count (eos/hpf) from baseline to week 24	5	8
	Absolute change in EoEHSS mean grade score from baseline to week 24	6	9
	Absolute change in EoEHSS mean stage score from baseline to week 24	7	10
	Absolute change in EoE EREFS total score from baseline to week 24	11	12
	Proportion of patients achieving peak esophageal intraepithelial eosinophil count of $< 15$ eos/hpf at week 24	13	14
	NES for the relative change from baseline to week 24 in the EoE diagnostic panel (EDP) transcriptome signature	15	17
	NES of the relative change from baseline to week 24 in the type 2 inflammation transcriptome signature	16	18

#### 5.6.4. Subgroup Analysis

Subgroups described in Section 3.5 for the primary and key secondary efficacy endpoints (as listed in Section 4.4.1 and Section 4.4.2) will be summarized. Treatment difference and its 95% confidence interval in subgroups of patients will be presented in forest plots. Interactions between the subgroups and treatment groups will be tested.

#### 5.6.5. Analysis of Exploratory Efficacy Variables

The analysis of other efficacy variables will be the same as the primary analysis described in Section 5.6.1 Section 5.6.2.

The prorated and un-prorated DSQ scores will be analyzed using the same method as the co-primary endpoint of absolute change from baseline in DSQ. Descriptive statistics and the CDF plots will also be provided for adults and adolescents separately.

#### 5.7. Analysis of Safety Data

The analysis of safety and tolerability will be performed on the SAF, as defined in Section 3.2.

The safety analysis will be based on the reported AEs, clinical laboratory evaluations, vital signs and 12-lead ECG.

Thresholds for treatment-emergent Potential Clinically Significant Values (PCSVs) in laboratory variables, vital signs and ECG are defined in Section 11.3. Treatment-emergent PCSV is any PCSV developed or worsened in severity compared to the baseline during the treatment and follow-up period. When identifying treatment-emergent PCSVs in Part C, baseline is the last available valid measurement taken prior to the first dose of extended active treatment in Part C (scheduled to be administered at week 24 visit [visit 11]).

The time interval to detect any event or abnormality is between the first injection of study medication and EOS.

The summary of safety results will be presented for each study part by treatment received in the corresponding part. For safety variables/summaries involving baseline values, e.g., absolute change from baseline or shift table, study part specific baselines will be used. Summaries for Part B will use the study baseline (i.e., the latest available valid measurement prior to the first dose of study drug in the study). Summaries for Part C and follow-up period will use Part C baseline (i.e., the last available valid measurement prior to the first dose of extended active treatment in Part C).

In addition, the summary of safety results (including TEAEs, clinical laboratory, vital signs and ECG) will be performed for subjects who were impacted by COVID-19 pandemic and not impacted by COVID-19 pandemic in each study part, respectively.

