### 1.2.2. Secondary Objectives

The secondary objectives of the study are:

- To evaluate the safety, tolerability, and immunogenicity of dupilumab treatment for up to 52 weeks in adult and adolescent patients with EoE
- To explore the relationship between dupilumab concentration and responses in adult and adolescent patients with EoE, using descriptive analyses
- To evaluate the molecular effects of dupilumab on transcriptomic signatures associated with EoE and type 2 inflammation
- To demonstrate the efficacy of dupilumab treatment compared with placebo after 24 weeks and 52 weeks of treatment in adult and adolescent patients with EoE who have previously received swallowed topical corticosteroids

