### 2.1. Study Design and Randomization

Part B is a 24-week treatment, randomized, double-blind, placebo-controlled study phase to determine the treatment effect of dupilumab compared with placebo in adult and adolescent patients with EoE as assessed by histological and clinical measures. After a screening period up to 12 weeks, patients were centrally randomized via interactive web response system (IWRS) in a 1:1:1 ratio to dupilumab 300 mg SC QW, dupilumab 300 mg SC Q2W or placebo SC and treated double-blind for 24 weeks in Part B. Randomization was stratified by age ( $\geq 18$  vs.  $\geq 12$  to  $< 18$  years of age) and use of PPI at randomization (yes vs. no). At the end of Part B, eligible patients were to be provided an option to enter Part C, which consists of a 28-week period of active treatment with dupilumab. Patients from Part B who were randomized to placebo during the double-blind treatment period would be re-randomized in a 1:1 ratio to dupilumab 300 mg QW or dupilumab 300 mg Q2W. Patients from Part B who were randomized to dupilumab during the double-blind treatment period would remain on the same dupilumab treatment in Part C. Treatment assignment in Part C were managed by an interactive web response system (IWRS) to maintain blinding of treatment assignment in Part B. All patients would be followed up for an additional 12 weeks after completing Part C. Patients in Part B who do not enter Part C would enter a 12-week follow-up period immediately after Part B. Patients who participated in Part A were not eligible to participate in Part B.

Approximately 210 patients (70 per treatment group) are planned to be randomized in Part B from multiple global sites.

The design of the overall study is depicted below in [Figure 1](#). As Part A and Part B are carried out as 2 separate sub-studies with no overlap in patients, Part A and Part B will each have a separate 2-sided alpha level of 0.05.

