#### Secondary endpoints in Part C:

Secondary endpoints assessed in Part C (through week 52) will be summarized with descriptive statistics for Part C SAF patients who entered Part C from Part B by the treatment groups received in Part C, as well as based on the treatment assignment in Part B (as randomized). Descriptive statistics will include number of patients, mean, median, Q1, Q3, standard deviation, minimum, and maximum for continuous efficacy variables; and patient counts and proportions for categorical efficacy variables. No formal statistical hypothesis testing will be performed. Inferential statistics will only be provided as needed.

All observed values, regardless of whether rescue treatment is used or data are collected after withdrawal from study treatment, will be used for analysis. No missing values will be imputed.

For categorical efficacy variables, the proportion of patients meeting response criteria at each visit will be calculated using the number of patients with non-missing value at the visit as the denominator.

For efficacy variables whose calculations involve baseline values, e.g., absolute (or percent) change from baseline, separate summaries will be provided for analyses using the study baseline and Part C baseline values. The study baseline is the latest available valid measurement taken prior to or on the date of the first dose of study drug administration (scheduled to be administered at the baseline visit [visit 3]). Part C baseline is the last available valid measurement taken prior to or on the date of the first dose of extended active treatment (scheduled to be administered at week 24 visit [visit 11]). For DSQ, Part C baseline; is defined in section 6.4; if it is missing, the latest available DSQ score prior to first Part C injection will be Part C baseline.

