Lymphocytes	>4.0 Giga/L and ≤ 4.0 Giga/L at baseline	<0.6 Giga/L and ≥0.6 Giga/L at baseline  >6.0 Giga/L and ≤6.0 Giga/L at baseline	<0.6 Giga/L and ≥0.6 Giga/L at baseline (adolescents only)  >4.0 [ $>6.0$ ] Giga/L and ≤4.0 [ $\leq 6.0$ ] Giga/L at baseline

Parameter	Adults (≥18) a	Adolescents (≥12 to <18) a	Combined
Neutrophils	<1.5 Giga/L and ≥1.5 Giga/L at baseline (Non-Black); <1.0 Giga/L and ≥1.0 Giga/L at baseline (Black)	<1.2 Giga/L and ≥1.2 Giga/L at baseline >ULN and baseline ≤ ULN	<1.5 Giga/L and ≥1.5 Giga/L at baseline (Non-Black); <1.0 Giga/L and ≥1.0 Giga/L at baseline (Black) [ <1.2 Giga/L and ≥1.2 Giga/L at baseline]  >ULN and baseline ≤ ULN (adolescents only)
Monocytes	>0.7 Giga/L ≤ 0.7 Giga/L at baseline	>1.2 Giga/L and ≤ 1.2 Giga/L at baseline	>0.7 [1.2] Giga/L ≤ 0.7 [1.2] Giga/L at baseline
Basophils	>0.1 Giga/L ≤ 0.1 Giga/L at baseline	NONE	>0.1 Giga/L ≤ 0.1 Giga/L at baseline (adults only)
Eosinophils	(>0.5 Giga/L and >ULN) and (≤0.5 Giga/L or ≤ ULN at baseline)	(>0.5 Giga/L and >ULN) and (≤0.5 Giga/L or ≤ ULN at baseline)	(>0.5 Giga/L and >ULN) and (≤0.5 Giga/L or ≤ ULN at baseline)
Hemoglobin	≤115 g/L and > 115 g/L at baseline for male; ≤95 g/L and > 95 g/L at baseline for Female.  ≥185 g/L and <185 g/L at baseline for Male; ≥165 g/L and < 165 g/L at baseline for Female  Decrease from Baseline ≥20 g/L	<100 g/L and ≥100 g/L at baseline  ≥200 g/L and <200 g/L at baseline	≤115 g/L and > 115 g/L at baseline for male; ≤95 g/L and > 95 g/L at baseline for Female. [ <100 g/L and ≥100 g/L at baseline]  ≥185 g/L and <185 g/L at baseline for Male; ≥165 g/L and < 165 g/L at baseline for Female [≥200 g/L and <200 g/L at baseline]  Decrease from Baseline ≥20 g/L
Hematocrit	≤0.37 v/v and > 0.37 v/v at baseline for Male ; ≤0.32 v/v and > 0.32 v/v at baseline for Female  ≥0.55 v/v and < 0.55 v/v at baseline for Male ; ≥0.5 v/v and < 0.5 v/v at baseline for Female	≤0.37 v/v and >0.37 v/v at baseline for Male; ≤0.33 v/v and >0.33 v/v at baseline for Female  ≥0.52 v/v and <0.52 v/v at baseline for Male; ≥0.47 v/v and <0.47 v/v at baseline for Female	≤0.37 v/v and > 0.37 v/v at baseline for Male ; ≤0.32 [≤0.33] v/v and > 0.32 [≥0.33] v/v at baseline for Female  ≥0.55 [≥0.52] v/v and < 0.55 [≤0.52] v/v at baseline for Male ; ≥0.5 [≥0.47] v/v and < 0.5 [≤0.47] v/v at baseline for Female

Parameter	Adults (≥18) a	Adolescents (≥12 to <18) a	Combined

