Respiratory rate	<12 per minute and ≥12 per minute at baseline  >20 per minute and ≤20 per minute at baseline	<12 per minute and ≥12 per minute at baseline  >20 per minute and ≤20 per minute at baseline	<12 per minute and ≥12 per minute at baseline  >20 per minute and ≤20 per minute at baseline
Weight	≥5% increase from baseline ≥5% decrease from baseline	≥5% weight loss from baseline	≥5% increase from baseline (adults only) ≥5% decrease from baseline
ECG			Ref.: CPMP 1997 guideline.
HR	≤50 bpm and decrease from baseline ≥20 bpm ≥120 bpm and increase from baseline ≥20 bpm	≤50 bpm and decrease from baseline ≥20 bpm ≥120 bpm and increase from baseline ≥20 bpm	≤50 bpm and decrease from baseline ≥20 bpm ≥120 bpm and increase from baseline ≥20 bpm
PR	≥220 ms and increase from baseline ≥20 ms	≥200 ms and < 200 ms at baseline	≥220 ms and increase from baseline ≥20 ms [≥200 ms and < 200 ms at baseline]
QRS	≥120 ms & < 120 ms at baseline	≥110 ms & < 110 ms at baseline	≥120 [≥110] ms and < 120 [<110] ms at baseline

Parameter	Adults (≥18) a	Adolescents (≥12 to <18) a	Combined
QTc	Absolute values (ms)	Absolute values (ms)	Absolute values (ms)
Borderline	Borderline:	Borderline:	Borderline:
Prolonged	431-450 ms and < 431ms at baseline for Male;	431-450 ms and < 431ms at baseline for Male;	431-450 ms and < 431ms at baseline for Male;
Additional	451-470 ms and < 451 ms at baseline for Female	451-470 ms and < 451 ms at baseline for Female	451-470 ms and < 451 ms at baseline for Female
	Prolonged:	Prolonged:	Prolonged:
	>450 to <500 ms and ≤ 450 ms at baseline for Male;	>450 to <500 ms and ≤ 450 ms at baseline for Male;	>450 to <500 ms and ≤ 450 ms at baseline for Male;
	>470 to <500 ms and ≤ 470 ms at baseline for Female	>470 to <500 ms and ≤ 470 ms at baseline for Female	>470 to <500 ms and ≤ 470 ms at baseline for Female
	Additional:	Additional:	Additional:
	≥500 ms and < 500 ms at baseline	≥500 ms and < 500 ms at baseline	≥500 ms and < 500 ms at baseline
	Increase from baseline	Increase from baseline	Increase from baseline
	Borderline: Increase from baseline 30-60 ms	Borderline: Increase from baseline 30-60 ms	Borderline: Increase from baseline 30-60 ms
	Prolonged: Increase from baseline >60 ms	Prolonged: Increase from baseline >60 ms	Prolonged: Increase from baseline >60 ms

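### For patients who stay on dupilumab, the safety baseline resets at week 24, so change from the pre-dupilumab value to week 52 is collected but not summarised

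*SAP*

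**What the plan says.** SAP 5.7 gives the general rule, "For safety variables/summaries involving baseline values, e.g., absolute change from baseline or shift table, study part specific baselines will be used", and applies it twice. For change and shift tables: "Summaries for Part C and follow-up period will use Part C baseline". For PCSVs: "When identifying treatment-emergent PCSVs in Part C, baseline is the last available valid measurement taken prior to the first dose of extended active treatment". The study baseline is used for Part B summaries only. No exception is made for patients whose treatment does not change at week 24, yet SAP 2.1 states: "Patients from Part B who were randomized to dupilumab during the double-blind treatment period would remain on the same dupilumab treatment in Part C". SAP section 5 reports these patients as the Q2W/Q2W and QW/QW groups.

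The rule agrees with protocol 10.5, which defines baseline separately for each study part.

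The objectives cover a longer span. SAP 1.2.1 names safety and efficacy after up to 52 weeks as the Part C primary objective, and SAP 1.2.2 lists as a secondary objective: "To evaluate the safety, tolerability, and immunogenicity of dupilumab treatment for up to 52 weeks in adult and adolescent patients with EoE".

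For Part C efficacy variables that involve a baseline, SAP 5.6.2 plans both comparisons: "separate summaries will be provided for analyses using the study baseline and Part C baseline values".

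**The concern.** For the QW/QW and Q2W/Q2W groups the Part C baseline follows about 24 weeks of dupilumab. A change measured from it describes only the second part of their exposure. The first part is described separately in the Part B tables, and no planned table joins the two within the patient. These are the patients with about 52 weeks of exposure starting from a pre-dupilumab value, so they carry most of the information for the 52-week objective. SAP 5.5.2 will report their total dupilumab exposure across Parts B and C, next to safety changes that never span more than one part.

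A gradual change that stays below a change-based PCSV limit in each part would be counted in neither, even when the total is well above the limit. ECG shows the gap plainly. It is scheduled at screening, week 24 and week 52, and the comparison of screening with week 52 is not planned.

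**Working it through.** **Inputs.** The plan states no figure that needs reproducing. The change-based PCSV limits come from SAP 11.3: haemoglobin "Decrease from Baseline ≥20 g/L"; weight "≥5% decrease from baseline"; creatinine, a change of 30% or more; QTc, an increase of 30 to 60 ms (borderline category) or more than 60 ms (prolonged). Planned arm size is 70 (SAP 2.3).

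**Method.** Take one change just below the limit in Part B and another in Part C. Add absolute changes and multiply ratios. Then check that the absolute limit for the same parameter is not crossed.

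| Parameter | Study baseline → week 24 → week 52 | Part B | Part C | Total | Change limit | Absolute limit |
|---|---|---|---|---|---|---|
| Haemoglobin, adult male (g/L) | 155 → 136 → 117 | −19 | −19 | −38 | fall of 20 | 115 or below: not reached |
| Creatinine, adult (µmol/L) | 60 → 77 → 100 | 77/60 = 1.283, +28.3% | 100/77 = 1.299, +29.9% | 100/60 = 1.667, +67% | 30% | 150 or above: not reached |
| Weight (% of study baseline) | 100 → 95.1 → 90.4 | −4.9% | −4.9% | 0.951² = 0.904, −9.6% | 5% | none |
| QTc, female (ms) | 380 → 409 → 438 | +29 | +29 | +58 | 30 (borderline) | 451 (borderline): not reached |

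None of these sequences meets that parameter's own criteria in either part under the reset baseline. Against the study baseline, each meets its change limit by week 52. The most that can go unflagged is just under 1 − 0.95² = 9.75% for weight loss and just under 1.30² − 1 = 69% for creatinine. In whole units it is 19 + 19 = 38 g/L for haemoglobin and 29 + 29 = 58 ms for QTc. The rows are illustrations, not predictions. A related parameter may still flag the same patient: haematocrit, for example, has its own absolute limit.

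**Number affected.** Two arms of 70 give 140 as a ceiling. With the 15% dropout assumed in SAP 2.3, 140 × 0.85 = 119, and the Part C exclusion criteria may lower this further.

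**Safety and efficacy side by side.** Protocol 10.4.3.2.2 sets only a Part C baseline for Part C efficacy, and SAP 5.6.2 adds the study baseline. Protocol 10.5 sets a per-part baseline in general, and SAP 5.7 adds nothing for safety.

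**Follow-up.** SAP 3.2 defines a follow-up period for patients who did not enter Part C. SAP 5.7 gives all follow-up summaries the Part C baseline, defined as the last value before the first Part C dose. These patients have no such dose, so the rule gives them no baseline.

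**The case against.** The case against has several sound parts.

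- A reader might infer that 52-week change is never measured. The documents do not support that. Values are collected before treatment and through week 52, and SAP 5.7.2 to 5.7.4 tabulate results by visit as well as changes. The gap is in the planned summaries. The tabulated means do not fill it, because they come from different sets (Part B SAF and Part C SAF) and give no within-patient change, shift or PCSV count.
- A reader might infer that the SAP departs from the protocol. It does not: protocol 10.5 sets the per-part convention.
- A reader might infer that any slow drift escapes detection, for instance that QTc could rise 60 ms in each part without a flag. It could not, because 60 ms falls in the borderline category each time. Many SAP 11.3 limits are absolute thresholds (ALT, AST, electrolytes, platelets and others), and a patient who crosses one is flagged in the part where that first happens. Only change-based criteria miss sub-threshold drift.
- Adverse event reporting does not depend on these baselines. Investigators review all laboratory values, and protocol 9.4.5 says when an abnormal result becomes an adverse event. Nothing in the documents suggests that drift in haemoglobin, creatinine, weight or QTc is expected.
- SAP 5.7 looks for abnormalities from first injection to end of study, and SAP 5.7.2 and 5.7.3 allow other tabular and graphical methods. The first sets a time window and leaves the baseline reset in place. The second permits a further display but does not commit to one.

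These points reduce the size of the problem. They do not supply the missing comparison.

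**Conclusion.** The point holds in limited form. Under SAP 5.7, patients who take dupilumab in both parts have no planned laboratory, vital-sign, weight or ECG change, shift or PCSV summary that runs from the pre-dupilumab value to week 52, although two objectives concern safety up to 52 weeks. It applies to at most about 140 patients, or about 119 under the SAP's dropout assumption. It bears on change and shift tables generally, and on PCSV counts where the criterion is change-based and no absolute limit is crossed.

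The finding rests on reading SAP 5.7 as the complete rule for safety baselines; no other section of either document adds a study-baseline display for Part C safety. Safety output is descriptive, so alpha, power and the efficacy conclusions are untouched. For placebo/dupilumab patients the Part C baseline is the right one. This is a cheap improvement, not a defect that puts the trial's main conclusions at risk.

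**What to change.** In SAP 5.7, for patients who received dupilumab in Part B and continue it in Part C, add change-from-baseline, shift and treatment-emergent PCSV summaries against the study baseline already defined in SAP 6.1. Run them through week 52, and through follow-up for the parameters collected there; the scheduled follow-up visit has no ECG. Keep the Part C baseline for placebo/dupilumab patients, and as a second display for the continuing groups, in line with SAP 5.6.2.

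State also that patients who enter follow-up directly from Part B are summarised against the study baseline.

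The cost is a short addition to SAP 5.7 and a repeat run of existing tables with a baseline that is already defined. No new data are needed. The downside is more safety tables.

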#### 5.7.1. Adverse Events

The number and proportion of patients reporting TEAEs will be summarized for Part B week 24 treatment period, Part C extended active treatment period, and follow-up period, as described in Section 3.2.

- For the summary of Part B treatment period, TEAEs with onset date during the Part B treatment period will be included. TEAEs that had an onset during the Part B treatment period and continued afterwards into Part C treatment period or the follow-up period will be counted only once as TEAEs during the Part B treatment period.
- For the summary of Part C extended treatment period, TEAEs with onset during the Part C extended treatment period will be included. TEAEs that had an onset during the Part C treatment period and continued afterwards into the follow-up period will be counted only once as TEAEs during the Part C extended treatment period.
- For the follow-up period, TEAEs with onset during the follow-up period will be included.

AE incidence tables will be presented by treatment group for the SAF as well as for selected subgroups. TEAE summaries will present the number (n) and percentage (%) of subjects experiencing an TEAE by SOC and PT, sorted by decreasing frequency of SOC and PT for the dupilumab treatment group. Multiple occurrences of AEs of the same PT (or SOC) in the same subject will be counted only once for that PT (or SOC). For tables presenting severity of events, the worst severity will be chosen for subjects with multiple instances of the same event. The denominator for computation of percentage is the number of patients in each treatment group for the corresponding analysis period as specified in Section 3.2.

An overall summary of TEAEs will be provided with number and proportions of patients with any:

- TEAE
- Serious TEAE
- TEAE of special interest (AESI)
- TEAE leading to death
- TEAE leading to permanent treatment discontinuation

Detailed summaries of TEAEs will include:

- TEAEs
  - TEAEs by SOC/PT
  - TEAEs by PT
  - TEAEs by SOC/PT with incidence of PT  $\geq 5\%$  in any treatment group
  - TEAEs by severity by SOC/PT
  - TEAEs related to study medication as assessed by the investigator by SOC/PT
  - TEAE of special interest by category (see Section 11.4)
- Serious TEAEs:
  - Serious TEAEs by SOC/PT
  - Serious TEAEs related to study medication as assessed by the investigator by SOC/PT
- TEAEs leading to permanent discontinuation of study treatment by SOC/PT
- Fatal TEAEs by SOC/PT

The time to first AESIs (TEAE by category) will be assessed by Kaplan-Meier estimates (K-M plot). Graphs of cumulative incidence rate over time will be presented by treatment group.

